1.1.2 Secondary

Secondary objectives are 1) determining preliminary evidence of any patterns of immunologic effects which differ by treatment including the immunologic effects of flutamide withdrawal on patients continuing on vaccine following a rising PSA on flutamide, 2) estimating toxicity noted on the arms and comparing the results, 3) evaluating, in a preliminary fashion, the effect of vaccine on development of metastatic disease after PSA progression, and 4) evaluating PSA responses and immune responses in patients who have had flutamide stopped at the time of PSA progression and either continue vaccine (Arm B) or have vaccine initiated (arm A) at time of flutamide discontinuation, 5) assessing response rate in patients randomized to both arms, as well as responses in those patients after cross over from the flutamide arm to vaccine only (time of disease progression will be defined as from the first date that vaccine is initiated in those patients who have had flutamide discontinued until the first notation of clinical progression).

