3 STUDY IMPLEMENTATION

3.1 Study Design (see Schema)

This randomized Phase II study proposes to evaluate the role of second line antiandrogen therapy and a pox vector based PSA vaccine in a population of patients with prostate cancer who have a rising serum PSA despite castrate levels of testosterone and prior antiandrogen therapy but no metastatic disease on bone or CT scans. Patients will be randomized on a 1:1 basis to Arm A (flutamide alone) or Arm B (flutamide + vaccine).

Arm A: Flutamide 250 mg orally TID beginning on day 1.

Arm B: Flutamide 250 mg orally TID beginning on day 1.

PROSTVAC-V/TRICOM (vaccinia) 2×10^8 pfu subcutaneously on day 1 of the first cycle only, followed by monthly (every 4 week) boosting vaccinations with PROSTVAC-F/TRICOM (fowlpox) 1×10^9 pfu subcutaneously on day 1 of each cycle. The duration of each treatment cycle is approximately 28 days.

[figure not shown]
Patients may continue on the therapy they were randomized to until the development of measurable disease on scans, rising serum PSA, or if they develop toxicity requiring stopping of their treatment. For patients with declining PSA no restaging will be done unless they develop symptoms consistent with metastatic disease. For patients with rising PSA, once 2 consecutive

PSA rises are seen from the last imaging studies, CT and bone scans will be done at their next scheduled visit. They will then be re-staged (CT and bone scans) at 3 month intervals as long as PSA continues to rise.

1. Patients on either arm who develop clinical progression (i.e. evidence of metastatic disease on scans) will be taken off study.
2. Patients who do not develop clinical progression (as defined above), but develop biochemical recurrence (i.e rising serum PSA levels) will undergo the following:
 - After 3 months of therapy, patients randomized to the flutamide alone (arm A) may cross over to receive vaccine if they develop a rising PSA and scans are without metastatic disease. The vaccine may commence 4 weeks after flutamide is stopped (if the PSA continues to rise. If there is an antiandrogen withdrawal response (a decline in PSA 28 days after the discontinuation of flutamide), PSA serum levels will be checked every 28 days and vaccine may commence when the serum PSA levels begin to rise (if scans are negative for metastasis and if patients continue to meet the eligibility criteria as outlined in section 2.1).

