5.4 Statistical Considerations

The primary objective of this randomized trial is to determine if use of a combination of vaccine plus flutamide may be associated with a trend toward improvement in time to treatment failure in patients with stage D0.5 prostate cancer compared to that which would occur with flutamide alone.

Secondary objectives are 1) determining preliminary evidence of any patterns of immunologic effects which differ by treatment including the immunologic effects of flutamide withdrawal on patients continuing on vaccine following a rising PSA on flutamide, 2) estimating toxicity noted on the arms and comparing the results, 3) evaluating, in a preliminary fashion, the effect of vaccine on development of metastatic disease after PSA progression, and 4) evaluating PSA responses and immune responses in patients who have had flutamide stopped at the time of PSA progression and either continue vaccine (Arm B) or have vaccine initiated (arm A) at time of flutamide discontinuation

The trial will be conducted as a randomized pilot trial with two arms as follows:

Arm A: flutamide

Arm B: flutamide + vaccine

Patients will be stratified based on a projected PSA doubling time (PSADT) of > 10 months vs. ≤ 10 months using the last 2 PSA values 1 month apart prior to enrollment on study.

$$\text{PSADT} = \frac{\log(2) \times t}{\log(\text{final PSA}) - \log(\text{initial PSA})}$$

t=time from initial to final PSA determination

$$\log(2) = 0.301$$

Time to treatment failure (TTF) will be the primary endpoint of this trial, where a treatment failure would be defined as a rising PSA (Bublely Criteria, JCO, 1999), development of metastatic disease, or removal from treatment due to excessive toxicity. Because PSA will be measured monthly and metastatic disease will be evaluated every 3 months, this will be sufficiently frequent for the primary evaluation to be made using standard actuarial methods (Kaplan-Meier plots with a log-rank p-value determinations).

The previously published trial of Nilutamide in a similarly eligible population of patients (stage

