Early stopping Rule- Should 2 patients in the first 10 patients enrolled on both arms of the trial exhibit a grade 4 toxicity of any type, regardless of the number of patients enrolled (from 2 to 10), then the trial will be temporarily closed to accrual to reevaluate the use of the agents in this combination. The exact upper 90% confidence bound about 2/10 is 45%, while that about 1/10 is 34%. Thus, while 1/10 is marginally consistent with one third of the patients having toxicity, 2/10 is consistent with more than this amount; thus 2 patients with toxicity early in the study are more than would be tolerated in a phase II study of this type.

Those patients who experience a PSA progression while on their initial, randomized therapy will stop flutamide treatment when this is determined. If they were randomized to receive vaccine + flutamide, they will begin to receive vaccine (alone), and if randomized to flutamide alone, they will start vaccine alone instead. The time to development of metastatic disease from the date of discontinuation of flutamide will be evaluated as a secondary endpoint for each arm, using Kaplan-Meier curves. Descriptive analyses of the pattern of change in PSA over time will also be performed.

It is expected that approximately 20-25 patients per year may be enrolled onto this trial. Thus, in order to obtain 66 evaluable patients, accrual of approximately three years will be expected. In order to allow for a very small number of patients who are inevaluable early after enrollment, the accrual ceiling will be set at 70 patients.

Following amendment F, the study will be continue to be randomized in a 1:1 fashion, and will enroll 31 eligible patients on each of the two arms (62 total), in order to have 80% power to detect a difference between a hypothesized median TTF of 10.0 months on flutamide alone and an increase of 8 months, to 18.0 months, with flutamide + vaccine, using a one-tailed 0.1 alpha level test. This difference assumes that patients enrolled on the study will be equally divided between those who have progressed on combined androgen therapy as well as those who have just begun combined androgen therapy. This calculation was made using nQuery Advisor version 5, assuming 60 months accrual, an additional 24 months of follow-up for the last patient enrolled, and hazards of 0.0693 per month for flutamide alone and 0.0385 for flutamide and vaccine, with a resulting hazard ratio of 1.80.

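### Section 5.4's only separate metastasis analysis starts at flutamide stop, so its curves cannot show the effect of vaccine on metastasis

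*Combined protocol and SAP*

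**What the plan says.** Secondary objective 3, in sections 1.1.2 and 5.4, is "evaluating, in a preliminary fashion, the effect of vaccine on development of metastatic disease after PSA progression". The analysis offered for it in section 5.4 is: "The time to development of metastatic disease from the date of discontinuation of flutamide will be evaluated as a secondary endpoint for each arm", by Kaplan-Meier curves. No between-arm test is named, and metastasis is not analysed on its own from randomisation.

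Entry to that analysis is set by the preceding text: "Those patients who experience a PSA progression while on their initial, randomized therapy will stop flutamide treatment when this is determined". Arm B then goes on with vaccine alone. For Arm A, section 5.4 says "if randomized to flutamide alone, they will start vaccine alone instead". Section 3.1 is permissive and adds a delay: "The vaccine may commence 4 weeks after flutamide is stopped", and later still if PSA falls after withdrawal, subject to negative scans and continued eligibility.

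Objective 5 in section 1.1.2 has its own origin for patients who cross over: "time of disease progression will be defined as from the first date that vaccine is initiated in those patients who have had flutamide discontinued". It runs to clinical progression, which section 3.1 equates with metastasis on scans: "Patients on either arm who develop clinical progression (i.e. evidence of metastatic disease on scans) will be taken off study". Objective 5 is not repeated in section 5.4.

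**The concern.** Objective 3 names a causal quantity: "the effect of vaccine on development of metastatic disease after PSA progression". Two features of the section 5.4 analysis prevent its estimation.

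- **Selection.** A patient enters only once PSA has progressed. After Amendment F the trial is powered on the vaccine moving median time to treatment failure, of which PSA rise is a component, from 10 to 18 months. If it does, fewer Arm B patients enter, and they enter later after randomisation.
- **No comparator.** After the origin both arms are planned to be on vaccine. Whatever separates the curves is not vaccine versus no vaccine.

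A vaccine with no effect on metastasis could appear to shorten the interval to metastasis, and a vaccine that delays metastasis could show no difference. The comparison that randomisation does support, vaccine at entry versus vaccine deferred to PSA progression, is not planned for metastasis.

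Objective 4 (PSA and immune responses after flutamide stop) has a related problem. Arm B stays on vaccine through flutamide withdrawal, while Arm A waits at least 4 weeks. A PSA fall due to withdrawal therefore happens on vaccine in Arm B and before vaccine in Arm A. No baseline is given for either arm.

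**Working it through.** **1. The plan's own figures (section 5.4, Amendment F).** Hazards are ln 2/10 = 0.0693 and ln 2/18 = 0.0385 per month, ratio 1.80. With accrual A = 60 and follow-up F = 24 months, P(event) = 1 − [e^(−λF) − e^(−λ(A+F))]/(λA), giving 0.955 and 0.845. Expected events are 31 × (0.955 + 0.845) = 55.8. Schoenfeld power at one-sided 0.10 is Φ(√55.8/2 × ln 1.80 − 1.282) = Φ(0.914) = 0.82. The stated 80% reproduces. No size or power is stated for metastasis.

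**2. Who enters, by hand.** Assume constant, independent hazards and no vaccine effect on metastasis. The share with PSA failure first is then (metastasis median)/(metastasis median + failure median). With a 30-month metastasis median this is 30/40 = 75% in Arm A and 30/48 = 62.5% in Arm B. With 9 months it is 9/19 = 47% and 9/27 = 33%. The sets differ even in this simplest case, although the median time from flutamide stop to metastasis is then equal in both arms.

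**3. Simulation with no vaccine effect on metastasis.** PSA failure is exponential with medians 10 and 18 months. Metastasis time is m × (E/ln 2)^(1/k), with E standard exponential, m the median and k the Weibull shape. The two times are joined by a Gaussian copula with correlation ρ. A patient enters if PSA failure comes first, and the gap is metastasis time minus PSA failure time. Section 1.2.1 cites medians of 9.0 and 30 months, and 30% with metastasis at 9 months (exponential median 9 × ln 2/−ln 0.7 = 17.5). Shape and correlation are assumptions; the documents give neither. For k = 2 and ρ = 0.4:

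| Metastasis median (months) | Enter, A | Enter, B | Median gap, A | Median gap, B | B shorter by |
|---|---|---|---|---|---|
| 9 | 44% | 26% | 4.3 | 3.8 | about 0.4 |
| 17.5 | 70% | 47% | 9.8 | 8.4 | about 1.4 |
| 30 | 87% | 68% | 19.6 | 16.6 | about 3.0 |

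With k = 1 and ρ = 0 the gap difference is nil. With a falling hazard (k = 0.8, median 30) it favours Arm B by about 1.5 months at ρ = 0 and is close to zero at ρ = 0.4.

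A second model, with a shared gamma frailty (variance 0 to 1), gave a B/A hazard ratio of about 1.00 for a constant metastasis hazard and 1.04 to 1.12 for a rising one. Entry was 40–81% in Arm A and 26–65% in Arm B. From randomisation the same data gave 0.99 to 1.01.

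**4. Two limiting cases.** Take a patient with PSA failure at 10 months and metastasis at 30, a gap of 20. If vaccine delays only PSA failure by 8 months, the gap is 30 − 18 = 12, an apparent harm. If it delays both by 8 months, the gap is 38 − 18 = 20, and a real benefit disappears.

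**5. What the randomisation origin could detect.** Assumptions: 31 per arm, 60 + 24 months, one-sided 0.10, 80% power, exponential times, no losses. Solve √d/2 × ln HR = 1.282 + 0.842, with d the events expected under that ratio:

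| Control median (months) | Events | Detectable HR (A/B) |
|---|---|---|
| 9 | about 57 | 1.75 |
| 17.5 | about 47 | 1.86 |
| 30 | about 35 | 2.05 |

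**The case against.** The plan is modest on this point. Objective 3 is labelled preliminary, and section 5.4 plans per-arm curves without a test, whereas it names a log-rank p-value for the primary endpoint. No false-positive claim is built in, and a hazard ratio of 1.00 to 1.12 would be lost in sampling noise with about 31 patients per arm, not all of whom enter. All of this stands. But the preliminary label concerns how firm the evidence is. It does not supply an unvaccinated comparator or undo the selection.

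A reader might infer that sections 1.1.2 and 5.4 give conflicting definitions of one endpoint. They do not. The flutamide-stop origin serves objective 3 in both arms, and the first-vaccine origin serves objective 5 in crossover patients, for whom it is an ordinary choice. Both lead to the same event in those patients, so the text should say which origin belongs to which objective.

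A reader might also infer that withdrawal PSA falls in Arm B would be credited to vaccine. Objective 4 makes no such attribution; what is missing is a baseline and a common rule.

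Finally, metastasis from randomisation is not a clean outcome either. After week 12, scans follow PSA rises or symptoms, so detection depends on the PSA course. Some patients also leave the study for toxicity (sections 3.3 and 5.3). This stands and limits the fix.

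**Conclusion.** The point holds. Followed as written, the flutamide-stop curves cannot show an effect of vaccine on metastasis, because entry is a post-randomisation outcome that the vaccine is meant to delay and both arms are then planned to receive vaccine. That conclusion needs no simulation.

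The size does. Under shape 2 and correlation 0.4, a vaccine with no effect on metastasis looks worse by about 0.4 to 3.0 months across the medians cited in section 1.2.1. It would be too strong to say that the vaccine will look harmful, or that the false gap vanishes only when metastasis is memoryless and independent of PSA failure: with a falling hazard the gap can be near zero without either condition, or can favour Arm B. The lower entry in Arm B is the stable finding; it appeared in every scenario run. The primary endpoint and its sample size are not affected.

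**What to change.** 1. In section 5.4, add as a secondary analysis time from randomisation to first metastasis in all randomised patients by assigned arm. Use Kaplan-Meier curves and a log-rank test, which may be stratified by the randomisation factors (section 5.4 does not now specify a stratified test). Describe it as immediate versus deferred vaccine, not vaccine versus none.
2. Label the flutamide-stop curves (objective 3) and the first-vaccine curves for crossover patients (objective 5) descriptive, with no between-arm inference. State one origin per objective, and say whether flutamide stops for toxicity enter the flutamide-stop analysis.
3. For objective 4, take PSA at flutamide stop as baseline in both arms and report withdrawal-period falls the same way in both.
4. Reconcile the passages on Arm A vaccine after PSA progression: section 5.4 says it will start, section 3.1 says it may, after a delay, and objective 4 places it at flutamide discontinuation.
5. State the ascertainment limits: scans triggered by PSA or symptoms after week 12, and exits for toxicity.

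The cost is wording in sections 1.1.2 and 5.4. No new procedure is needed, since section 3.1 lets patients who stop treatment for PSA progression stay on study until metastasis. Precision will remain limited, as calculated above.

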5.5 Multi-Institutional Guidelines

IRB Approvals:

The NCI IRB must approve the addition of each participating site to the protocol and will require a copy of the local IRB approval from each participating site before NCI IRB approval will be granted.

Each site will need the local approval of their IRB in order to participate in this trial; in addition protocol changes will need to be communicated in accordance to with their local practice.

Participating institution will provide the NCI PI with copies of the initial local IRB approvals and semi-annual or annual continuing review approvals. The NCI PI will then furnish these to the NCI IRB. Registration will be halted at any participating institution in which a current continuing approval is not on file at the NCI IRB. Only one version of the protocol will be the correct version; amendments must be initiated through the coordinating center; amendments will be submitted to the NCI IRB and to the IRB of participating institution. The center will be responsible for its own IRB submissions.

Amendments and Consents:

The NCI PI will provide the NCI IRB with copies of all amendments, consents and approvals from each participating institution.

Patient Registration:

Participating institution must register patients with the CCR Central Registration as specified under section 2.3. Such patients will be treated, monitored, and managed according to the guidelines of this protocol, after signing a current version of the informed consent. A copy of the registration checklist and off-study forms should be faxed to Coordinating Center Research Team at [contact].

Agent Ordering and Agent Accountability:

NCI supplied agents may be requested by the Principal Investigator (or their authorized designee) at each participating institution. Pharmaceutical Management Branch (PMB) policy requires that agent be shipped directly to the institution where the patient is to be treated. PMB does not permit the transfer of agents between institutions (unless prior approval from PMB is obtained.) The CTEP assigned protocol number must be used for ordering all CTEP supplied investigational agents. The responsible investigator at each participating institution must be registered with CTEP, DCTD through an annual submission of FDA form 1572 (Statement of Investigator), Curriculum Vitae, Supplemental Investigator Data Form (IDF), and Financial Disclosure Form (FDF). If there are several participating investigators at one institution, CTEP supplied investigational agents for the study should be ordered under the name of one lead investigator at that institution.

Active CTEP-registered investigators and investigator-designated shipping designees and ordering designees can submit agent requests through the PMB Online Agent Order Processing (OAOP) application < <https://eapps-ctep.nci.nih.gov/OAOP/pages/login.jsp> >. Access to OAOP requires the establishment of a CTEP Identity and Access Management (IAM) account < <https://eapps-ctep.nci.nih.gov/iam/> > and the maintenance of an “active” account status and a “current” password. Alternatively, site personnel can fax completed Clinical Drug Requests (NIH-986) to the Pharmaceutical Management Branch at [contact]. For questions about drug orders, transfers, returns, or accountability, call [contact] Monday through Friday between 8:30 am and 4:30 pm (ET) or email [contact] anytime.

Agent Inventory Records - The investigator, or a responsible party designated by the investigator, must maintain a careful record of the inventory and disposition of all agents received from DCTD using the NCI Drug Accountability Record Form (DARF). (See the NCI Investigator’s Handbook for Procedures for Drug Accountability and Storage.)

Contact information: Pharmaceutical Management Branch (<http://ctep.cancer.gov>) [name], [contact], [contact].

Data Collection and Toxicity Reporting:

Participating institution must submit research and clinical data to the Coordinating Center of the Center for Cancer Research, NCI on a monthly basis. Data will be entered into the C3D database at participating facilities, training of designated data entry staff will be provided. Required data to be entered into C3D and/or maintained at the study site include, not exclusively:

prior disease related therapies, with dates, disease type, stage, disease sites, lab results, RECIST measurements, ECG, Scan reports and images on CD, and adverse events. Supporting eligibility source documentations should be reviewed and the eligibility checklist for registration needs to be sent within 3 business days to the Coordinating Center for eligibility review.

Concurrent medications need to be entered into the database.

All > grade 2 adverse events at least possibly attributed to research and not in the consent must be submitted as soon as possible so that they may be reported to the NCI IRB within 7 days of receipt (see section 7.1). Reporting to local IRB should be done as stipulated by local IRB guidelines. All data collection forms and records may be audited on-site at participating institutions and should be made available at the time of the study audit.

CTEP Multicenter Guidelines:

CTEP will perform a site visit every 3 years at participating facilities.

This protocol will adhere to the policies and requirements of the CTEP Multicenter Guidelines. The specific responsibilities of the Principal Investigator and the Coordinating Center (Study Coordinator) and the procedures for auditing are presented in **APPENDIX G**.

- The Principal Investigator/Coordinating Center is responsible for distributing all IND Action Letters or Safety Reports received from CTEP to all participating institutions for submission to their individual IRBs for action as required.
- Except in very unusual circumstances, each participating institution will order DCTD-supplied agents directly from CTEP. Agents may be ordered by a participating site only after the initial IRB approval for the site has been forwarded by the Coordinating Center to the CTEP PIO ([contact]) except for Group studies.

5.6 Data Safety Monitoring Plan

5.6.1 Principal Investigator/Research Team

The clinical research team will meet on a regular basis when patients are being actively treated on the trial to discuss each patient. Decisions about dose level enrollment and dose escalation if applicable will be made based on the toxicity data from prior patients.

All data will be collected in a timely manner and reviewed by the principal investigator or a lead associate investigator. Adverse events will be reported as required in section 7. Any safety concerns, new information that might affect either the ethical and or scientific conduct of the trial, or protocol deviations will be immediately reported to the IRB using iRIS and if applicable to the Sponsor.

The principal investigator will review adverse event and response data on each patient to ensure safety and data accuracy. The principal investigator will personally conduct or supervise the investigation and provide appropriate delegation of responsibilities to other members of the

research staff.

The members of the site specific research team will review all adverse events for each subject in this trial in a timely manner. Unexpected adverse events and/or serious adverse events will be reported to the NCI's Institutional Review Board (IRB), site specific IRB and Cancer Therapy Evaluation Program (CTEP) (see section 7.1.1). The study PI will review all safety data. If trends are noted and/or risks warrant it, accrual will be interrupted and/or the protocol and/or consent will be modified accordingly. In addition, the data will be reviewed regularly by the drug monitor at CTEP.

